3.0 Scientific Endpoints

The primary endpoint is the reduction of discounting of the future, weight loss, and improved glycemic control.

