7.0 Inclusion and Exclusion Criteria

Inclusion:

Participants must be 18 years of age or older to participate.

Prediabetes: Participants must have a diagnosis of prediabetes within the last 2 years or meet criteria for prediabetes. The American Diabetes Association guidelines (Group, 2003) defines prediabetes as Fasting Plasma Glucose (FPG) 100-125 mg/dl, 2h glucose 140-199 mg/dl after Oral Glucose Tolerance Test (OGTT), or hemoglobin A1c (HbA1c) approximately 5.4-6.7%.

Exclusion:

Type 2 Diabetes: Individuals will be excluded if they have Type 2 Diabetes.

Pregnancy: Women who are pregnant or lactating will be excluded from participation.

Substance use, abuse, or dependence: Individuals that currently have problems with substance dependence, addiction, or problematic substance use that would limit participation (e.g., binge drinkers, alcoholics, daily stimulant/opiate users) will be excluded.

Conditions that affect adherence: Participants should not have a condition that would limit participation which include medical conditions that would affect individuals' ability to use the computer for prolonged period of time; leave the individual unable to ambulate; or current diagnoses of an eating disorder other than binge-eating disorder (anorexia, bulimia), unmanaged psychiatric disorder (depression, anxiety, attention deficit hyperactivity disorder (ADHD), schizophrenia), or an intellectual impairment that would impact study adherence. Additionally, participants should be able to attend to all or most group and individual sessions. If a participant is not able to make most sessions (e.g. participant is out of town for several days or weeks during the study (e.g. work or vacation travel)) they may be excluded from the study

Abnormal glucose related to medications: Participants should not be taking medications that would limit participation and cause abnormal glucose levels (e.g. atypical antipsychotic medications or glucocorticoids) including diabetic drugs such as Metformin.

Prior participation in similar studies: Individuals who have recently participated in a laboratory study using similar methods may also be excluded.

Recent changes in weight: Individuals should not have had any significant changes in weight (e.g. 10% change) prior to starting this study.

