16.0 Withdrawal of Subjects

Subjects who do not adhere to the protocol procedures and study instructions may be withdrawn from research analyses, as determined by the Principal Investigator and/or NIH Data Safety Committee. In addition to not adhering to study instructions, possible reasons for removal may include nonsystematic responding to questionnaires and HbA1c (blood sugar) levels that are not in the study prediabetes range. If a participant is withdrawn from the study without their consent, they will be debriefed about the nature of the study and be compensated for the amount of time spent in the study. We may also stop an ongoing session, or end participation in the study because we have collected all the information we need.

Participants will be debriefed about the nature of the study and the reason for their removal. No additional follow-up is needed.

Participants can withdraw from the research at any time. If participants withdraw, no further data will be collected, but any information that had been provided may be retained by the researcher and analyzed.

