17.0 Risks to Subjects

There may be some sensitivity associated from certain questions asked when filling out questionnaires or having body measurements taken and subjects might feel uncomfortable disclosing some personal information such as medical history. Subjects can refuse to answer any questions that they are not comfortable

answering. Subjects will be free to withdraw from the study at any time, and their refusal to continue will not affect other medical care provided at any healthcare facility.

Participants may experience hunger due to refraining from eating before the session. Feelings of hunger will subside when the participant is able to eat after the. In addition, only personnel certified in CPR, first aid, and AED will conduct study sessions and these individuals are trained to contact appropriate medical personnel in the event of an emergency.

Breach of confidentiality is another potential risk. The studies will occur in our facilities at the University at Buffalo and the Virginia Tech Carilion Research Institute. To protect confidentiality, we will use only ID numbers and keep all data in locked cabinets or in locked offices and password protected electronic files in password protected computers. Any data shared between sites will involve de-identified data only and files will be encrypted or password protected. These screening, monitoring, and confidentiality procedures have been in effect for more than 10 years and for more than 2,000 subjects across the various protocols employed by our group.

Participants may have a small bruised area on the finger from the pinprick site. The bruise should fade over time without treatment. If during the course of the study, a subject's blood glucose exceeds the range for prediabetes (Fasting Plasma Glucose (FPG) 100-125 mg/dl, or 2h glucose 140-199 mg/dl after Oral Glucose Tolerance Test (OGTT) or hemoglobin A1c (HbA1c) 5.4-6.7%), that subject may be directed to his or her physician or other medical care provider for further evaluation.

Participants may have their blood pressure measured. If during the course of the study, a subject's blood pressure reaches hypertensive crisis (180/110 mmHg), that subject may be directed to his or her physician or other medical care provider for further evaluation.

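### Section 16.0 does not confine the HbA1c-range removal reason to the period before randomisation, so as written a randomised participant who improves to below 5.4% can be taken out of the analyses

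*Combined protocol and SAP*

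**What the plan says.** - **Removal (Section 16.0).** The paragraph opens with "Subjects who do not adhere to the protocol procedures and study instructions may be withdrawn from research analyses". It leaves the decision to the trial's own leadership or its safety body: "as determined by the Principal Investigator and/or NIH Data Safety Committee". It then adds that "possible reasons for removal may include nonsystematic responding to questionnaires and HbA1c (blood sugar) levels that are not in the study prediabetes range". No visit, direction or arm is specified, and nothing says that the decision is made blind to arm.
- **After removal (Section 16.0).** "No additional follow-up is needed". Keeping the data already collected is addressed only for people who leave by their own choice: "If participants withdraw, no further data will be collected, but any information that had been provided may be retained by the researcher and analyzed".
- **The range (Section 7.0).** One entry route is "hemoglobin A1c (HbA1c) approximately 5.4-6.7" percent. The others are a prediabetes diagnosis in the past 2 years, fasting glucose, or a 2-hour glucose tolerance result.
- **The outcome (Sections 2.0 and 3.0).** "The primary endpoint is the reduction of discounting of the future, weight loss, and improved glycemic control". Aim 2 expects a larger HbA1c reduction in BT-EFT.
- **Timing (Section 11.0).** Randomisation takes place at about week 6 of treatment. HbA1c is measured at baseline, 3 months and 6 months.
- **High values during the study (Section 17.0).** For a value above the range, "that subject may be directed to his or her physician or other medical care provider for further evaluation". Values below the range are not mentioned.
- **Analysis (Section 14.0).** Factorial ANCOVA. No analysis set, intention-to-treat statement or missing-data rule is given.

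**The concern.** A range that defines who may enter is normally finished with once a participant is randomised. Here the same range reappears as a ground for removal, with no end point, and the variable it acts on is one the intervention is meant to lower. A participant who goes from 5.6% to 5.2% has done what Aim 2 hopes for and now also meets a listed ground for removal.

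This differs from removal for poor adherence, because a fully adherent responder is caught. Presence in the data set would depend on the outcome itself. If the treatment works, more people cross the lower limit in the better arm, so an evenly applied clause discards more of that arm's best results. Blinding the decision would prevent selective use but not this effect.

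The same people could also disappear from the weight and delay-discounting comparisons. Someone removed at 3 months might never supply 6-month values, which no later analysis could recover.

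**Working it through.** **The plan's own figure.** The only sample-size calculation (Section 14.0) is for delay discounting: standardised difference 0.72, power 0.80, alpha 0.05. The normal approximation gives n = 2(1.96 + 0.842)²/0.72² = 30.3, so 31 per arm. The t-test calculation gives 31.3, so 32 per arm and 64 in total, as stated. The 78 to be recruited leave 78 × 0.8 = 62.4 after 20% attrition, slightly under 64, whereas 64/0.8 = 80. Section 6.0 instead expects about 80 completers, so whether there is slack for further removals depends on which section is followed. The documents give no mean, SD or effect for HbA1c, so everything below rests on assumed values.

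**Step 1: does the mechanism exist?** Take the 6-month value as normal in each arm and keep only 5.4-6.7%. With a = (5.4 − μ)/σ and b = (6.7 − μ)/σ, the retained mean is μ + σ[φ(a) − φ(b)]/[Φ(b) − Φ(a)]. For BT mean 5.7, BT-EFT mean 5.5 and SD 0.3:

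| Arm | Removed | Retained mean |
|---|---|---|
| BT | 16% | 5.786 |
| BT-EFT | 37% | 5.680 |

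The difference falls from 0.20 to 0.106. Over BT means of 5.6-6.0% and SDs of 0.3-0.4, 41-78% of the difference remains. Almost all of the loss comes from the lower limit: cutting only at 6.7% leaves 88-100%. This compares raw 6-month means. Change scores or baseline adjustment lose less, as Step 2 shows.

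**Step 2: every participant out of range at 6 months is removed and the value dropped.** Two assumed models, each with a true difference of 0.20:

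| Model | Removed or below 5.4%, BT | Same, BT-EFT | Estimate |
|---|---|---|---|
| A: entry mean 5.7-5.9, SD 0.3, cut to 5.4-6.7; change −0.1 and −0.3; SD of change 0.2-0.3 | 10-23% | 26-42% | 0.134-0.171 (change score); 0.115-0.160 (baseline-adjusted) |
| B: entry mean 5.7-5.9, SD 0.3, within-person SD 0.15, fall common to both arms 0-0.2 | 4-27% | 14-53% | 0.125-0.170 (baseline-adjusted) |

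The smallest loss is (0.20 − 0.171)/0.20 = 14.5% and the largest is (0.20 − 0.115)/0.20 = 42.5%, so about 15-40%.

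**Step 3: the clause is applied to the 3-month value only** (model B, about half of the change reached by then). It removes 4-18% of BT and 8-29% of BT-EFT. The estimate is 0.187-0.193, a loss of 0.007/0.20 = 3.5% to 0.013/0.20 = 6.5%, so about 3-7%.

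**Step 4: partial use at 6 months** (model A).

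| Share of out-of-range participants removed | Estimate | Loss |
|---|---|---|
| Half | 0.178-0.189 | about 5-11% |
| A quarter | 0.191-0.196 | about 2-5% |

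**Step 5: boundary cases.** With a true difference of 0 and even-handed removal, the estimate stays at 0. With no removal, it returns 0.200. If values up to and including the triggering one are kept, the loss is small or nil.

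**The case against.** The strongest reply is that the clause concerns screening. Consent is signed before the screening HbA1c (Sections 9.0 and 11.0). Section 6.0 counts people as enrolled although only about a quarter are expected to pass in-lab screening. Section 19.0 pays for the screening visit, and Section 11.0 uses the range as an eligibility check. On that reading Section 16.0 covers consented but ineligible people, Section 17.0 covers later high values, and the two do not conflict. This is plausible and may be what the authors meant. But the clause does not say so. It stands beside non-adherence to study instructions, in a paragraph that begins with exclusion from analysis, and nothing in Section 14.0 overrides it.

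A second reply is that the wording is doubly permissive. That is right, and it limits the size: full removal at 6 months is an upper scenario. It does not remove the problem, because unguided discretion over a primary outcome makes the direction of bias unpredictable.

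A reader might go further and infer that the plan directs removal of responders, or that the HbA1c result must be biased toward zero by 15-40%. The documents support neither. Removal is only a possibility, and the direction requires a true benefit and even-handed use. The percentages come from assumed values. The models also cut everyone's entry value at 5.4-6.7%, whereas Section 7.0 admits people by other routes.

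**Conclusion.** The point holds as an unbounded clause that permits exclusion on a primary outcome after randomisation. It does not show that such exclusion was intended or will happen.

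If the clause is applied alike in both arms, BT-EFT truly lowers HbA1c, and removed participants' values are left out, the HbA1c difference is understated. The assumed range runs from about 3-7% (3-month value only) to about 15-40% (everyone out of range at 6 months removed). Losses are smaller under partial use and small or nil if values up to removal are kept. Uneven use could bias the result in either direction. With no true effect and even-handed use there is no bias. Weight and delay discounting could lose the same participants, but no size was computed for them. The ambiguity in the text is certain; its numerical effect is not.

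**What to change.** State in Sections 14.0 and 16.0 that:

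1. the HbA1c range is used only to judge eligibility before randomisation, alongside the other entry routes in Section 7.0, so that someone eligible by another route is not excluded by this wording;
2. no HbA1c value obtained after randomisation removes a participant from the analyses;
3. all randomised participants are analysed as randomised, with every collected HbA1c, weight and delay-discounting value kept.

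The boundary should be randomisation (about week 6), not the baseline assessment.

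Separately, reconcile Section 16.0 (possible removal) with Section 17.0 (possible referral) for out-of-range values during the study. Whether such a participant continues in treatment is a clinical matter for the sponsor, and the analysis statements above do not settle it.

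The cost is a few sentences. No new measurements, visits or participants are needed.

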2.0 Hypotheses

Specific Aim 1: To determine whether change in weight loss is superior for those with prediabetes randomized to behavioral treatment for obesity + EFT (BT-EFT) versus behavioral obesity treatment (BT). We hypothesize that weight loss for BT-EFT will be superior to BT after 6 months of treatment.

Specific Aim 2: To determine whether change in HbA1c is superior for those with prediabetes randomized to behavioral treatment for obesity + EFT (BT-EFT) versus behavioral treatment (BT). We hypothesize that reductions in HbA1c for BT-EFT will be superior to BT after 6 months of treatment.

Specific Aim 3: To determine whether change in DD is superior for those with prediabetes randomized to behavioral treatment for obesity + EFT (BT-EFT) versus behavioral treatment (BT). We hypothesize that reductions in DD for BT-EFT will be superior to BT after 6 months of treatment.

Secondary Aim 1: To determine whether change in medication and behavioral adherence for hypertension and/or hyperlipidemia medications is superior for those with prediabetes randomized to behavioral treatment for obesity + EFT (BT-EFT) versus behavioral treatment (BT). We hypothesize that medication and behavioral adherence for BT-EFT will be superior to BT after 6 months of treatment.

Secondary Aim 2: To determine whether improvements in working memory are superior for those with prediabetes randomized to behavioral treatment for obesity + EFT (BT-EFT) versus behavioral treatment (BT). We hypothesize that working memory improvements for BT-EFT will be superior to BT after 6 months of treatment.

Exploratory Aim 1: To examine the relationship between baseline DD and DD change with weight loss, improvements in HbA1c and medication adherence. We hypothesize that baseline DD and DD change will predict weight loss, improvements in HbA1c and medication adherence.

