Physical Activity: Physical activity may be measured using the Actigraph WGT3X-BT accelerometer. Participants will be shown how to properly wear the monitors and will be asked to wear their monitors for about a week. Data will be collected at a rate of 30 Hz and converted to one minute epochs for data analysis. Total activity counts and activity in the moderate to vigorous (MVPA) and vigorous (VPA) ranges will be estimated. Physical activity may be measured using a Fitbit (San Francisco, CA) or other activity monitor.

Subjective Hunger: Participants will be asked to provide subjective ratings of their hunger. Hunger will be assessed using a 5-point Likert scale (anchored by 1-Extremely Full and 5-Extremely Hungry).

Subjective Preferences: Participants may be asked to provide subjective ratings of their food/activity preferences by ranking, rating their liking using a 5-point Likert scale (anchored by 1-Do not like and 5-Like very much), and making choices between their food/activity.

Cue Attention: A Likert-style scale assessing attentiveness to the episodic cues and vividness cues during tasks will be assessed on a scale from 1 to 5, where 1 indicates "not at all" and 5 indicates "very much".

Delay Discounting: An operational definition of impulsivity is delay discounting, the degree to which a person will discount the value of a larger delayed reward in favor of a smaller immediate reward. Computerized/ experimenter administered assessments will provide participants with choices between a smaller amount of a hypothetical commodity available immediately or a larger amount available later. Participants will make choices between rewards such as money, food, physical activity, and health gains. Two methods may be used to measure discounting, Adjusting Amount and Adjusting Delay.

Adjusting Amount Discounting. The magnitude of the immediate commodity is adjusted until it is subjectively equivalent to the later larger amount. Subjective equivalence will be obtained at delays such as; 1 day, 1 week, 1 month, 3 months, 6 months, and 1 year. To ensure comparison between money and non-monetary rewards, prior to running the discounting programs for food, physical activity and health, participants will indicate the amount of the commodity whose receipt “right now” would be equally valuable to the participants as receiving a set amount of money, for example \$100. Participants may be presented with their EFT cues before making decisions at each delay period.

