14.0 Statistical Analysis Plan

Analytic plan is to use factorial ANCOVA to compare between group differences in different measures of DD, executive function, weight loss, changes in metabolic control, dietary composition, and physical activity for subjects randomly assigned BT-EFT/BT. Covariates will be used if significant differences between groups are observed in subject characteristics. We predict a main effect of EFT such that EFT will reduce the discounting, improve metabolic control, and increase weight loss compared to BT subjects.

The estimated sample size for this study is based on an ESD for reducing DD of 0.72 in obese/overweight subjects. In our pilot study of EFT vs control in a weight control program we observed even larger ESD of 1.64 for weight and 1.04 for energy intake. Based on ESD = 0.72 for DD, using power of 0.80 and alpha of 0.05, we can detect differences between groups in DD with 32 subjects per group, 64 total. Since we are anticipating 20% attrition for the field study, we will recruit 78 persons with prediabetes to start.

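### Section 16 allows a randomized participant to be removed from all analyses for undefined nonsystematic questionnaire responding, so valid weight and HbA1c data can be lost

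*Combined protocol and SAP*

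**What the plan says.** Section 16.0 lets the principal investigator and/or a data safety committee take subjects out of the analyses. Besides failure to follow study instructions, it says that "possible reasons for removal may include nonsystematic responding to questionnaires"; an HbA1c outside the study range is also listed. For people removed in this way it states that no further follow-up is required. A later sentence, on keeping and analysing data already given, is written for participants who withdraw themselves.

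Section 3.0 makes three outcomes primary: "The primary endpoint is the reduction of discounting of the future, weight loss, and improved glycemic control". For delay discounting (DD), Section 2.0 states the aim as a relative reduction: "We hypothesize that reductions in DD for BT-EFT will be superior to BT after 6 months of treatment".

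Section 12.0 describes two DD tasks. In Adjusting Amount, "The magnitude of the immediate commodity is adjusted until it is subjectively equivalent to the later larger amount". Adjusting Delay is a five-trial task that yields a k-value. Section 14.0 sizes the trial on DD and plans a factorial ANCOVA. It names no analysis set and does not say how missing or unusable DD records are handled.

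**The concern.** A doubtful set of answers is a problem of one instrument at one visit, but the removal in Section 16.0 acts on the person. Weight and HbA1c are measured objectively and do not become less valid because a questionnaire was answered erratically. Randomization is at about week 6 (Section 11.0), so the rule can operate on randomized participants, and the decision may be made by someone who knows the arm. Two things are at stake: the randomized comparison for weight and HbA1c, and protection against exclusions that are related, even unintentionally, to arm or outcome. A secondary possibility is that an undefined term could be stretched to cover records with very little discounting, which would tie removal to a primary outcome.

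**Working it through.** **1. What the rule reaches.**

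| Question | What the documents give |
|---|---|
| Unit of removal | The subject, from the analyses (16.0) |
| Automatic? | No, discretionary (16.0) |
| Definition of nonsystematic | None (12.0, 14.0, 16.0) |
| Decision blind to arm | Not required (16.0) |
| Limited to before randomization at about week 6 | No (11.0, 16.0) |
| Limited to the affected measure | No (16.0) |
| Analysis set that keeps the person | None (14.0) |
| Is a DD task a questionnaire? | Unclear: 11.0 lists DD measures apart from questionnaires; 12.0 puts the five-trial DD task inside the Coronavirus Questionnaire |

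The loss of weight and HbA1c follows from the other rows whichever way the last one is settled.

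**2. The plan's own sample size.** Section 14.0 is "based on an ESD for reducing DD of 0.72 in obese/overweight subjects" and, "using power of 0.80 and alpha of 0.05", states that "we can detect differences between groups in DD with 32 subjects per group, 64 total". A two-sample t-test with d = 0.72 and two-sided alpha 0.05 (sidedness is not stated) needs 31.27, so 32 per group; power at 32 is 0.809. The plan adds: "Since we are anticipating 20% attrition for the field study, we will recruit 78 persons with prediabetes to start". Now 78 × 0.80 = 62.4 completers, for power 0.80. The figure reproduces, but it allows for attrition only, not for removals by the investigator.

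**3. Fewer participants.** The documents give no rate, so 5% to 20% of 32 per arm is assumed. Power is from the noncentral t.

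| Removed | n per arm | Power, DD (0.72) | Power, weight (1.64) |
|---|---|---|---|
| 0% | 32 | 0.81 | >0.999 |
| 5% | 30 | 0.78 | >0.999 |
| 10% | 29 | 0.77 | >0.999 |
| 15% | 27 | 0.74 | >0.999 |
| 20% | 26 | 0.72 | >0.999 |

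The 1.64 is the pilot effect for weight in Section 14.0; no HbA1c effect is given. If the DD record is unusable, the DD loss occurs whether the person or only the score is dropped, so the DD column is not a cost specific to this rule.

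**4. Hypothetical: near-flat DD records removed.** Assume a normal DD score with SD 1, mean 0 in BT and −0.72 in BT-EFT, and removal of everyone below one common cutoff c. Choose c so that 20% of BT-EFT falls below it: c = −0.72 − 0.842 = −1.562.

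- Share of BT removed: Φ(−1.562) = 0.059.
- With a = c − μ and λ = φ(a)/(1 − Φ(a)), the remaining mean is μ + λ and the remaining SD is √(1 + aλ − λ²).
- BT-EFT: λ = 0.350, mean −0.370, SD 0.764.
- BT: λ = 0.125, mean 0.125, SD 0.888.
- d = 0.495 / √((0.764² + 0.888²)/2) = 0.60. With 25.6 and 30.1 left, power is 0.59.

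Removing 5% of BT-EFT in the same way takes out about 1% of BT and gives d = 0.68, power 0.75.

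A second model assumes hyperbolic discounting, a BT mean ln k of −4 to −6, SD 1.5 to 2, and a flag when 1/(1+k) − 1/(1+365k) < 0.10. At mean −5 and SD 2 it gives 6% v 20% flagged, d = 0.60 and power 0.58. Across the whole range, d runs from 0.70 to 0.53 and power from 0.78 to 0.42.

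**The case against.** The strongest reply is that Section 16.0 grants a permission and prescribes nothing: removal may never be used, and it names questionnaires, which Section 11.0 lists apart from DD measures. That stands against any claim that an unusable DD record automatically costs a participant's weight and HbA1c. It does not answer the point that undefined discretion over exclusion after randomization is itself the weakness.

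A reader might also infer three stronger things, none of which the documents support.

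- *Flat responders will be removed, mostly from BT-EFT, and Aim 3 is biased toward no difference.* No section calls flat responding nonsystematic or requires value to fall with delay. The stated aim is less discounting, not none, and a flat record can be scored. The cutoff, the 10% flag and the ln k values in step 4 are assumptions.
- *No DD score is possible without orderly indifference points.* That concerns Adjusting Amount only. Adjusting Delay gives a k-value from five trials.
- *The rule makes the trial underpowered for weight.* At the pilot effect it does not, and for HbA1c there is no effect size from which to judge.

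**Conclusion.** The point holds in a limited form. As written, the rule permits whole-person, unblinded, undefined removal after randomization, and nothing in Section 14.0 counteracts it. This rests on the text alone. Its size cannot be fixed, because no rate of nonsystematic responding is given and removal is discretionary. What is at risk is the integrity of the weight and HbA1c comparisons; no power loss has been shown for them. The possible dependence on the DD outcome is left open by the missing definition, but it is not something the plan prescribes. The fall from 0.72 to 0.60 illustrates assumed inputs and is not an estimate for this trial. The sample-size calculation is not at fault. The change should be made because it is cheap and closes both routes.

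**What to change.** In Section 16.0, delete nonsystematic responding as a reason for removing a participant from analyses. In Section 14.0, add:

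> All randomized participants are analysed in their assigned group for weight, HbA1c and every other available measure. Nonsystematic responding is judged per task and visit by a fixed rule applied without knowledge of arm, and affects only that score. Low or no discounting is not by itself nonsystematic. The main DD analysis includes all scorable records, using the score suited to each task (Adjusting Amount or Adjusting Delay). Excluding flagged scores is a sensitivity analysis.

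The fixed rule should be written down before unblinded data are seen. The other reasons for removal from analyses in Section 16.0 would then have to be reconciled with the first added sentence. The cost is wording in two sections and one sensitivity analysis. The downside is that some noisy DD scores remain in the main analysis.

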Measurements for blood HbA1c, blood pressure, cholesterol, height and weight measured to calculate BMI, measures of delay discounting, food demand, other executive functions (e.g. working memory), energy intake, physical activity, and medication adherence will be collected at baseline, 3 months, and 6 months. In response to the coronavirus mandatory closures, these assessment measures may also be recorded remotely. In the event that a participant must have assessment measures performed remotely, a staff member may conduct a conference call or video conference with the participant to instruct them on how to complete questionnaires and complete executive function tasks online via online survey (For example, on Qualtrics). The staff member may also instruct the participant on how to weigh themselves and observe the participant taking their weight at home via video conference. In order to collect A1c measures for remote

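### Section 16.0 ends follow-up for randomised participants whom the team removes, so their 6-month outcomes are lost for reasons tied to adherence or to an endpoint

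*Combined protocol and SAP*

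**What the plan says.** Section 16.0 describes two ways out of the study.

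- **Removal by the team.** The section opens with "Subjects who do not adhere to the protocol procedures and study instructions may be withdrawn from research analyses", at the discretion of the principal investigator or the safety committee. Other possible reasons are nonsystematic questionnaire responses and "HbA1c (blood sugar) levels that are not in the study prediabetes range". Removed participants are debriefed, and then "No additional follow-up is needed".
- **Withdrawal by the participant.** "If participants withdraw, no further data will be collected, but any information that had been provided may be retained by the researcher and analyzed".

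No section describes a participant who stops the programme, or is taken off it, and still attends assessments.

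Section 3.0 sets the outcomes at stake: "The primary endpoint is the reduction of discounting of the future, weight loss, and improved glycemic control". The hypotheses in Section 2.0 concern 6 months of treatment. Section 11.0 places assessments at baseline, 3 months and 6 months, and randomisation after about 6 weeks of treatment. For coronavirus closures it adds that "these assessment measures may also be recorded remotely": weight observed by video, a mailed HbA1c kit and online tasks. It also offers an optional 12-month visit by video for HbA1c, delay discounting (DD) and weight.

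Section 14.0 plans a factorial ANCOVA and allows for 20% attrition. It names no analysis population and no method for missing outcomes.

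**The concern.** The trial asks what adding EFT does among those randomised. Under Section 16.0, whether a removed participant has a 6-month value depends on events after randomisation.

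- **Non-adherence** is partly a response to the assigned arm. BT-EFT participants have cue tasks that BT participants do not.
- **Out-of-range HbA1c** is a value of one of the three primary outcomes. Section 16.0 gives the reason neither a direction nor a time limit. As worded, it could remove a participant whose HbA1c fell below 5.4% on treatment as well as one whose HbA1c rose above 6.7%.

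Losing outcomes on such grounds can bias the comparison in either direction, and a larger sample does not cure it. The same section also lets non-adherent participants be taken out of the analyses. Even outcomes that were collected could therefore be set aside, and Section 14.0 has no rule on the analysis population to prevent this.

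**Working it through.** **Inputs.** From Section 14.0: effect size 0.72 SD for DD, power 0.80, alpha 0.05, 32 per group, 20% attrition, 78 recruited. From Section 11.0: randomisation at about week 6. From Section 19.0: payments of $30 and $40 for the 3- and 6-month sessions. The documents do not say how those lost would fare, so each value for that below is an assumption, shown over a range.

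**1. The plan's own figure.** A two-sided two-sample t-test with d = 0.72 needs 32 per group (power 0.809), which reproduces the plan. Exact allowance for 20% loss is 64 / 0.8 = 80. The stated 78 matches 32 × 1.2 = 38.4, rounded up to 39 per arm. The gap is small and is not the issue here.

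**2. How many lack a 6-month outcome.** 78 × 0.20 = 15.6, so about 16, if all planned attrition occurs after randomisation. About 31 per arm remain (78 × 0.80 = 62.4).

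**3. Completers against all randomised.** Assume loss p is equal in both arms, the effect in completers is 0.72 SD, and those lost keep no EFT benefit. Then:

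- all-randomised effect = 0.72 × (1 − p)
- overstatement by completers = 1 / (1 − p) − 1

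| Post-randomisation loss p | All-randomised effect (SD) | Overstatement |
|---|---|---|
| 10% | 0.648 | 11% |
| 20% | 0.576 | 25% |
| 30% | 0.504 | 43% |

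**4. No true effect, loss related to outcome in one arm.** Assume the true all-randomised difference is zero. Those lost from BT-EFT do worse than its completers by g SD, and loss in BT is unrelated to outcome. The completers' difference is then biased by p × g. The two-sided type I error at nominal 0.05, with 35, 31 or 27 analysed per arm, is:

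| p | Bias, g = 0.5 | Type I error | Bias, g = 1.0 | Type I error |
|---|---|---|---|---|
| 10% | 0.05 | 0.055 | 0.10 | 0.070 |
| 20% | 0.10 | 0.067 | 0.20 | 0.121 |
| 30% | 0.15 | 0.084 | 0.30 | 0.191 |

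If the extra loss fell in BT instead, the sign of the bias would reverse.

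**5. Power.** With 31 analysed per arm, power at 0.72 is 0.796. With all 39 per arm assessed, it is 0.881 if the effect stays at 0.72, and 0.709 if it is diluted to 0.576. The case for follow-up is therefore freedom from bias. It does not promise more power.

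**The case against.** The strongest reply is that Section 16.0 is narrower than it looks. Much of this stands.

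- **Stopping sessions.** A reader might infer that anyone who stops attending loses the 6-month assessment. The documents do not say so. Section 11.0 sets no attendance condition on the assessments and provides recordings for missed meetings. Someone who skips sessions, and is neither removed nor withdrawn, stays on schedule. Ending data collection is also proper for anyone who withdraws consent to it.
- **Recoverability.** A reader might infer that no analysis could help. Weight is taken at each treatment meeting, all three outcomes are due at 3 months, and data already given by those who withdraw may be kept. A model could use these under stated assumptions. Only later values are lost.
- **Adverse events.** A reader might infer that safety reporting stops. Section 15.0 records events as they are reported, and the optional 12-month visit repeats the questionnaire. What is lost is the scheduled questionnaire at 3 and 6 months.
- **Unequal burden.** Section 11.0 also prompts controls to log in and answer questions, and says their tasks are otherwise the same. Nothing in the documents shows that the arms will stop at different rates.
- **Attribution of the 20%.** The plan says only "Since we are anticipating 20% attrition for the field study". That may cover lost contact, withdrawn consent, or loss in the weeks before randomisation, which cannot bias the randomised comparison.
- **HbA1c removal.** This reason may be meant for screening. Section 17.0 answers a reading above the range during the study with referral to a physician, not removal. Section 16.0 does not limit the reason to screening, however.
- **Early release.** The clause that lets staff end participation once they have enough information stands beside the one on stopping a session. It does not say that it applies before month 6.

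One could add that follow-up which is not needed is not forbidden. Even so, the plan provides none for removed participants.

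**Conclusion.** The point holds for randomised participants removed by the team before month 6, and for the missing category of people who leave the programme but still consent to assessment. For those removed, the loss of 6-month DD, weight and HbA1c follows from a stated rule, and the grounds include post-randomisation behaviour and a primary outcome.

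The size depends on assumptions. With equal loss and no retained EFT benefit, the overstatement is 11% to 43% for losses of 10% to 30%, and 25% at the planned rate. These figures are an upper bound on what a change to Section 16.0 could correct, since part of the attrition may lie beyond its reach. The documents do not support reading the whole 20% as a product of this rule, nor any claim about which arm would be favoured. The planned power is not the problem, because the recruited number already allows for 20% loss.

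**What to change.** In Section 16.0, separate (a) stopping the programme or being removed from it and (b) withdrawing consent to data collection. Then:

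1. Invite every randomised participant in (a) to the 3- and 6-month assessments, with at least weight, HbA1c, DD and the adverse event questionnaire.
2. Extend the remote assessment wording in Section 11.0 beyond coronavirus closures to cover these participants.
3. Debrief them after the 6-month assessment, as Section 11.0 does for everyone else. Early debriefing does little harm now, because nothing later is collected. It would matter once assessments continue.
4. Keep them in the analysis as randomised. Replace the permission to drop participants from the analyses for non-adherence or out-of-range HbA1c arising after randomisation. State the analysis population and the handling of missing outcomes in Section 14.0. Without this step, the newly collected values could still be excluded.
5. Reconcile the new text with Sections 9.0, 11.0 and 17.0, which end participation after a positive pregnancy test. When a participant leaves the programme is not at issue here.

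**Cost.** Protocol and consent wording, more contact attempts, some home-measured values, and the price of the kits, which the documents do not give. Session payments are at most about 16 × ($30 + $40) = $1,120 on the 78 of Section 14.0. Section 6.0 instead expects about 80 completers after 20% drop-out, which implies 80 / 0.8 = 100 starting and 20 lost, or $1,400.
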